6.6 Early Termination or Suspension of Clinical Investigation

Both the Sponsor and Investigator reserve the right to terminate the clinical investigation at any time. After review of the clinical safety data and consultation with Principal Investigator, Sponsor will make a final determination on whether to terminate or suspend the study. In the event of premature termination or suspension of the study, the sponsor will promptly notify the investigational center and governing regulatory agencies and communicate a plan for orderly termination or suspension. Any subjects already enrolled in the study will still be followed up for 30 days.

6.7 Informed Consent Process

After a normal clinical assessment, the Principal Investigator may approach patients whom he or she feels may be suitable for entry into this clinical investigation. The Principal Investigator should introduce the patient or the patient's legally authorized representative to the clinical investigation by explaining the Clinical Investigation

Plan, procedures and objectives to the patient or his/her legally authorized representative. The Principal Investigator will then provide an information sheet describing the clinical investigation, potential discomforts, risks and benefits of participation. The patient or his/her legally authorized representative will have 24 hours to decide whether they wish to participate in this clinical investigation due to the criticality of the timing that the treatment is applied once the patient is on a mechanical ventilator.

Any queries that patients may have regarding this clinical investigation will be addressed appropriately by the Principal Investigator, or another member of the investigative team at the hospital. Patients or their legally authorized representatives will be instructed that they are free to obtain further information from the Principal Investigator at any time and that they are free to withdraw their consent and to discontinue their participation in the clinical investigation at any time without prejudice.

If the patient is willing to participate in the clinical investigation, he/she or his/her legally authorized representative must read, understand and sign the informed consent form. The Principal Investigator will also sign this at the same occasion. Two copies of the consent form will be made. The original signed consent form will be kept in the Investigation Site File. A copy will be kept in the subject's medical notes and a further copy provided to the subject or his/her legally authorized representative.

Since the subjects will be unconscious and mechanically ventilated at the time of the informed consent process should they regain consciousness they will be allowed to withdraw from the study if desired without any impact on their medical treatment. If subjects do regain consciousness during the treatment they will be asked to sign the informed consent form if they are able.

6.8 Study Design and Number of Observations

The study design includes a planned total of one to sites with up to 10 subjects per site. Defined data analysis will be conducted on enrolled and associated data.

6.9 Safety Endpoints

The secondary safety endpoints are the percentage of patients who receive safe and successful placement of the multipolar lead in the left and right phrenic nerve utilizing ultrasound guidance and the percentage of patients who experience one or more serious device/procedure-related adverse events during the study.

No formal hypothesis tests will be conducted; therefore, power and significance level are not relevant in this context. However, the sample size was chosen to provide sufficient data on the occurrence of adverse safety findings. According to Virzi (1992), 80% of all usability issues are detected with four or five subjects. With up to 10 to 16 humans, the percentage of problems detected is approximately 95% to 98% (with 30% probability of at least one event). (Ref: Virzi, RA. Refining the Test Phase of Usability Evaluation: How Many Subjects is Enough? Human Factors, 1992. 34(4), 457-468.).

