6. STUDY DESIGN & METHODOLOGY

The study will examine performance and safety as defined in primary and secondary endpoints listed in Section 10. A maximum of up to 20 subjects will be enrolled in the study at up to 2 sites with up to 10 subjects per site. The final number of patients enrolled in the study will be based upon the time duration of the study and the rate of enrollment. In the first two patients, the investigator will stimulate the left phrenic nerve only and conduct CMAP tests and nerve conduction test on both phrenic nerves prior to and at least 3 weeks after the stimulation. These subjects will be examined 30 days' post study, to confirm safety of this method of stimulation of the phrenic nerve before enrolling the remaining patients up to a total of 20 subjects. After successfully demonstrating 30 day follow up on the initial two patients, stimulation will occur in both the left and right phrenic nerves simultaneously for the remainder of the trial. Typically, stimulation will occur once every 3 to 5 breaths and this decision will be left to the discretion of the attending physician. Figure 2 outlines the protocol for placement of the leads.

[figure not shown]

Figure 2. Study Left and Right Phrenic Nerve Pacing

Stimulation will occur for a maximum duration of 48 hours. A number of evaluations will also be conducted to measure the ease of placing and removing the stimulation leads as well as the ability of the lead to accommodate positional changes made by or to the patient.

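### The usability benchmark in protocol section 6.9 does not show that the sample is sufficient for serious device- or procedure-related events, and no confidence interval is planned for them

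*Protocol*

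**What the plan says.** Protocol section 6.9 has two safety endpoints. One is the percentage of patients with safe, successful ultrasound-guided lead placement. The other is "the percentage of patients who experience one or more serious device/procedure-related adverse events during the study". The section sets testing aside: "No formal hypothesis tests will be conducted; therefore, power and significance level are not relevant in this context". It still claims adequacy, stating that "the sample size was chosen to provide sufficient data on the occurrence of adverse safety findings".

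The support offered is a usability-testing paper, from which the protocol takes that "80% of all usability issues are detected with four or five subjects". It goes on that, with 10 to 16 subjects, "the percentage of problems detected is approximately 95% to 98% (with 30% probability of at least one event".

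On size, protocol section 6 says "A maximum of up to 20 subjects will be enrolled in the study", with the final number left to study duration and enrolment rate. SAP section 2 uses the first two patients, stimulated on the left side only, for safety only, and its Table 3 lists ten further patients, P03 to P12.

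On reporting, SAP section 2 (Adverse Events) plans a percentage for serious related events, and SAP section 6 summarises all secondary endpoints descriptively. The same SAP section plans 95% confidence intervals for the capture rate and for the diaphragm-thickness slope.

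**The concern.** The benchmark and the endpoint measure different things. A usability problem that shows up in about three subjects in ten will almost surely appear in a sample of 10 to 16. A serious related event, such as a bad outcome from the nerve damage, pneumothorax or vagal stimulation listed in protocol section 13.1, could be much rarer, and a sample of this size could easily contain none. The documents give no rate for such events, so nothing links the 30% figure to the endpoint.

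What is at stake is how a clean result is read. The protocol classes this as a safety study (section 2), aims to evaluate preliminary safety (section 5) and calls it a first-in-human study that will help define a pivotal trial (section 13.3). A serious-event percentage of 0%, reported without an interval and after a statement that the sample was sufficient, would carry forward with no stated uncertainty.

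**Working it through.** **Inputs from the documents.** Rate 30%; 10 to 16 subjects; stated detection of about 95% to 98%; 80% with four or five subjects (all protocol section 6.9). Maximum of 20 subjects (protocol section 6). I add n = 12, the two left-only patients plus the ten in SAP Table 3.

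**Inputs assumed.** The documents give no expected rate of serious related events. I use 10%, 5% and 1% per patient to show a range.

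**Step 1. Reproduce the plan's figure.** Section 6.9 gives no formula. Reading the 30% as the chance that any one subject shows a given problem, detection is 1 − (1 − 0.30)^n = 1 − 0.7^n:

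- n = 4: 76.0%; n = 5: 83.2%. These bracket the cited 80%.
- n = 10: 1 − 0.0282 = 97.2%, against about 95% stated (2.2 points higher).
- n = 16: 1 − 0.0033 = 99.7%, against about 98% stated (1.7 points higher).
- n = 20: 1 − 0.0008 = 99.9%.

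Solving backwards, 95% at n = 10 implies a rate of 0.259 and 98% at n = 16 implies 0.217, so no single rate gives both ends exactly. If the rate varies between problems, the figures come close: a beta distribution with mean 0.30 and a + b = 20 (SD about 0.10; my assumption) gives 79.8% at n = 5, 94.3% at n = 10 and 98.3% at n = 16.

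**Step 2. Apply the same formula to rarer events.** Chance of seeing at least one event, 1 − (1 − p)^n:

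| n | p = 10% | p = 5% | p = 1% |
|---|---|---|---|
| 10 | 65% | 40% | 10% |
| 12 | 72% | 46% | 11% |
| 16 | 81% | 56% | 15% |
| 20 | 88% | 64% | 18% |

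For example, with 12 patients and a 5% rate, 0.95^12 = 0.54, so the event is missed 54% of the time.

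**Step 3. What rate does the sample detect with 95% probability?** Solving 1 − (1 − p)^n = 0.95 gives p = 1 − 0.05^(1/n): 25.9%, 22.1%, 17.1% and 13.9% for n = 10, 12, 16 and 20. Detection of about 95% therefore applies only to events that affect roughly one patient in seven (n = 20) to one in four (n = 10), or more.

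**Step 4. What would zero events show?** The exact two-sided 95% upper limit is 1 − 0.025^(1/n): 30.8%, 26.5%, 20.6% and 16.8% for n = 10, 12, 16 and 20.

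**The case against.** The strongest reply is that section 6.9 makes no power claim, disclaims hypothesis tests and belongs to a feasibility study. Nothing in the text says that a clean result rules out nearly all problems; protocol section 13.1 says that some risks may not yet be known. Safety oversight does not hang on this sentence either: the first two patients are stimulated on one side and followed for 30 days before others enrol, with ECG and x-ray checks and review of events. The phrase about adverse safety findings is broader than serious events, and a usability benchmark is at least arguable for the lead-placement endpoint. All of this stands and keeps the point minor. It does not meet the core: dropping the test makes power irrelevant but not precision, and the section still calls the data sufficient.

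Two stronger readings are tempting, and the documents support neither.

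- A reader might infer that 95% to 98% is a material arithmetic error that flatters the trial. The text says approximately, the printed values are about two points lower than a uniform 30% gives, the formula is my reading of an unclear parenthesis, and modest variation between problems nearly reproduces them.
- A reader might infer that 10 to 16 subjects conflicts with enrolment of 20. Twenty is a ceiling, 10 to 16 lies below it, and the 12 patients implied by the SAP fall inside that range.

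**Conclusion.** The point holds as a minor one about rationale and reporting. The benchmark in section 6.9 may describe common usability or lead-placement problems, but it does not show that the sample is sufficient for serious device- or procedure-related events. At an assumed 5% rate, a sample of 10 to 20 has a 40% to 64% chance of showing even one such event.

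The rates of 10%, 5% and 1% are assumptions, and the calculation treats patients as independent with a common rate. The conclusion does not depend on any one of them: without an expected rate in the documents, the 30% figure cannot be carried over to this endpoint. The upper limits after zero events need no assumed rate. The mismatch of about two points in the printed range is a small correction in the conservative direction.

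**What to change.** 1. In protocol section 6.9, limit the 30% statement to common usability problems. Reword the parenthesis, which read literally is not a per-subject rate, so that it states one, and give the formula. With a uniform 30% rate the figures are 97.2%, 99.7% and 99.9% for 10, 16 and 20 subjects.
2. Add the chance of seeing at least one serious related event at 10%, 5% and 1% for the planned number of patients, with the rates labelled as assumptions.
3. In SAP sections 2 and 6, report the serious-event percentage with an exact two-sided 95% confidence interval.

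The cost is some wording and one interval, with no change to design or enrolment. The downside for the sponsor is that the stated assurance for serious events becomes less favourable.

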6.10 Primary Performance Endpoint: Stimulation Pulse to Capture the Diaphragm

The ability of the stimulation pulse to capture the diaphragm will be assessed using WOB (Work of Breathing Measurements). A logistic regression model with successful capture as the outcome will be used. The model will include repeated measurements within a subject.

6.10.1 Model:

capture = (timepoint) (subject)

where subject is a random effect, and the outcome of capture is yes/no based on whether the stimulation captures the diaphragm.

6.10.2 Hypothesis:

H_0 : The proportion of capture is less than or equal to the performance goal (PG) of 90%.

H_0 : $\hat{p}_1 \leq PG$

H_A : The proportion of capture is greater than the performance goal of 90%.

H_A : $\hat{p}_1 > PG$,

where \hat{p}_1 is the estimated proportion of capture from the logistic model accounting for repeated measurements within a subject.

6.10.3 Sample Size:

The following assumptions were the basis for the sample size calculation for the performance endpoint evaluating stimulation capture of the diaphragm:

- Power: 80%
- 1-sided α : 0.025
- Performance goal: 90%
- Expected success rate: 97.5%

With an anticipated success rate of 97.5% and a performance goal of 90%, 80 observations would yield $\geq 80\%$ power. Note that, for the purposes of sample size calculations, the observations are assumed to be independent. However, the primary analyses will account for within patient correlation, as described below. Increasing the number of observations will increase the statistical power.

6.10.4 Methods:

The proportion of successful capture will be analyzed using a logistic regression model accounting for patient as a random effect. The null hypothesis will be tested comparing the lower bound of the 95% two-sided confidence interval for the estimated percent agreement to the performance goal of 90%. If the lower bound is greater than 90%, the null hypothesis will be rejected and the endpoint will be considered met.

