6.1 Study Data Analysis and Statistical Methods

In general, summary statistics will include the mean, median, standard deviation, minimum and maximum for continuous measures and the number and frequency for categorical measures. All analyses will be conducted using SAS v9.3 or greater (SAS Institute Inc., Cary, NC, USA). Sample size calculations were conducted using

PASS v14 (PASS 14 Power Analysis and Sample Size Software (2015). NCSS, LLC. Kaysville, Utah, USA, ncss.com/software/pass).

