In addition, there may be additional analyses conducted and other tables and graphs created for the final clinical study report based on the outcomes of the initial analyses and additional data points of interest.

An interim analysis may be run and this was allowed in the protocol. See Statistical Methodology section for greater details.

PRIMARY ENDPOINTS

The primary endpoints for the study relate to the ability of the therapy to mobilize the diaphragm and of the PEPNS system to stimulate specific levels of work of breathing.

- Capture of the Left and/or Right Phrenic Nerve > 80% with an output parameter of < 10.5 volts.
- WOB (Work of Breathing) kept between 0.2 Joules/L and 2 Joules/L for 80% of stimulated breaths.

The capture of the left and right phrenic nerve will be demonstrated during setup and by maintaining the WOB between 0.2 and 2 Joules/L. The stimulation voltage resultant from the tissue impedance and the user set current will be logged and evaluated to ensure it is less than 10.5 volts. Capture will also be evaluated in terms of synchrony.

The ability of the stimulation pulse to capture the diaphragm will be assessed using WOB (Work of Breathing Measurements). A logistic regression model with successful capture as the outcome will be used. The model will include repeated measurements within a subject.

Model:

$\text{capture} = (\text{timepoint}) (\text{subject})$

where subject is a random effect, and the outcome of capture is yes/no based on whether the stimulation captures the diaphragm.

Capture for this analysis is defined as synchrony of the stimulated breath with the output parameter < 10.5 volts and WOB between 0.2 and 2.0 Joules/L. Synchrony will be achieved if the lag time between start of inspiration and start of stimulation is less than 88 ms.

Hypothesis:

H_0 : The proportion of capture is less than or equal to the performance goal (PG) of 80%. Note: This hypothesis used a 90% performance goal in the protocol for the purposes of sample size calculation to ensure that there would be sufficient data to achieve the 80% performance goal when taking into account lost to follow up due to death, etc.

$H_0: \hat{p}_1 \leq \text{PG}$

H_A : The proportion of capture is greater than the performance goal of 80%.

$H_A: \hat{p}_1 > \text{PG}$,

where \hat{p}_1 is the estimated proportion of capture from the logistic model accounting for repeated measurements within a subject.

Sample Size:

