This sample size calculation reflects the use of a 90% performance goal as noted above in the hypothesis section and in the CIP. Again, this was done to ensure that there would be sufficient data to achieve the 80% performance goal when taking into account lost to follow up due to death, etc. The following

	PEPNS Study Statistical Analysis Plan <small>CONFIDENTIAL: THIS DOCUMENT AND ALL INFORMATION CONTAINED HEREIN IS PROPRIETARY TO STIMDIA MEDICAL, INC. AND IS NOT TO BE DISCLOSED WITHOUT THE EXPRESS WRITTEN PERMISSION OF STIMDIA MEDICAL, INC.</small>	Document Number SAP0001	Rev. Level 1
---	--	-----------------------------------	------------------------

assumptions were the basis for the sample size calculation for the performance endpoint evaluating stimulation capture of the diaphragm:

- Power: 80%
- 1-sided α : 0.025
- Performance goal: 90%
- Expected success rate: 97.5%

With an anticipated success rate of 97.5% and a performance goal of 90%, 80 observations would yield $\geq 80\%$ power. Note that, for the purposes of sample size calculations, the observations are assumed to be independent. However, the primary analyses will account for within patient correlation, as described below. Increasing the number of observations will increase the statistical power.

Methods:

The proportion of successful capture will be analyzed using a logistic regression model accounting for patient as a random effect. The null hypothesis will be tested comparing the lower bound of the 95% two-sided confidence interval for the estimated percent agreement to the performance goal of 80% (see note above). If the lower bound is greater than 80%, the null hypothesis will be rejected and the endpoint will be considered met.

If the logistic regression model does not converge (i.e. it does not provide reliable estimates of diaphragm capture), other methods will be used to characterize the capture rate. The method used will be dependent on the data and will be described in detail along with the reasons for using that method.

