6. STATISTICAL METHODOLOGY

STATISTICAL PROCEDURES

The primary statistical methods used in this study will be descriptive where continuous variable will be summarized using means, medians, standard deviation, minimums and maximums and categorical variables will be summarized using frequencies and percent for each categorical level.

The primary endpoint will be analyzed using a logistic regression where diaphragm capture (yes/no) is the dependent variable and time point and subject are the independent fixed effect and random effect predictors. The point estimate of the diaphragm capture rate will be estimated from logistic regression model along with a two-sided 95% confidence interval. The lower bound of that confidence interval will be compared to the performance goal of 80%. If the lower bound is above 80%, then the endpoint will have been achieved.

Secondary endpoints will be summarized as noted in the secondary endpoints section. Each endpoint will be summarized descriptively.

Additional evaluations will also be summarized descriptively. In addition, diaphragm thickness over time will be modeled using regression analysis. The slope parameter and 95% confidence intervals will be presented. Additional diaphragm thickness analyses may be run.

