11. PROGRAMMING PLANS

Synchrony will be measured by first finding when inspiration starts using the trigger flows for each subject/stimulation combination. Next the start of stimulation will be found using the trigger signal. The difference in time between the start of inspiration and the start of stimulation will be the lag time. This will be calculated for all stimulated breaths.

Work of Breath (WOB) is calculated by finding the end of stimulation using the trigger signal, waiting 100 msec, and then capturing the next 50 observations for WOB. Each set of 50 observations is summarized using the mode of the 50 observations. This is also done for each stimulated breath.

If the lag time is less than 88 msec, and the WOB is between 0.2 and 2.0 Joules/L, and the output parameter is less than 10.5 volts then capture will have been achieved and a binary indicator variable will be set to 1.0. If capture is not achieved, that binary indicator variable will be set to 0.0. This binary indicator variable will be used for analyzing the primary endpoint.

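### The stated power of at least 80% with 80 observations does not follow from the stated inputs: exact power is 67.7%, and no test that holds one-sided 0.025 reaches 80%

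*Protocol*

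**What the plan says.** Protocol 6.10.3 lists the inputs for the capture endpoint: power 80%, one-sided alpha 0.025, performance goal 90%, expected success rate 97.5%. It concludes: "With an anticipated success rate of 97.5% and a performance goal of 90%, 80 observations would yield" at least 80% power. It says openly that independence is assumed for this calculation, and adds: "Increasing the number of observations will increase the statistical power".

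The decision rule is in Protocol 6.10.4: "The null hypothesis will be tested comparing the lower bound of the 95% two-sided confidence interval for the estimated percent agreement" with the 90% goal. A lower bound from a two-sided 95% interval corresponds to one-sided 0.025, so rule and alpha agree.

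On method, Protocol 6.1 says only "Sample size calculations were conducted using" PASS v14. No test, formula or cut-off is named.

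SAP section 2 carries the same inputs and the same 80 observations forward ("This sample size calculation reflects the use of a 90% performance goal as noted above in the hypothesis section and in the CIP") but changes the goal that is tested. It explains: "This hypothesis used a 90% performance goal in the protocol for the purposes of sample size calculation", so that enough data would remain for an 80% goal after losses. SAP section 6 confirms the test: "The lower bound of that confidence interval will be compared to the performance goal of 80" per cent. The SAP states no power for that test.

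**The concern.** Every input needed to reproduce the power figure is given, and the figure does not reproduce. The gap matters because this is the only power statement in either document, and the SAP relies on it as assurance that there will be enough data. A reader would credit the protocol's 90% rule with a false-negative risk of at most 20% at the planned observation count, when under independence it is about 32%. In the SAP the figure also stands beside a test against a different goal, so it does not describe the analysis that will be run.

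**Working it through.** **Inputs** (Protocol 6.10.3, repeated in SAP section 2): n = 80 independent observations, p0 = 0.90, p1 = 0.975, one-sided alpha = 0.025, claimed power at least 0.80.

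**Step 1. Exact test.** Find the smallest r with P(X ≥ r | 80, 0.90) ≤ 0.025. Power is then P(X ≥ r | 80, 0.975).

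| Success if at least | Size at p0 = 0.90 | Power at p1 = 0.975 |
|---|---|---|
| 76/80 | 0.0880 | 95.0% |
| 77/80 | 0.0353 | 85.9% |
| 78/80 | 0.0107 | 67.7% |

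77/80 exceeds 0.025, so the cut-off is 78/80 and power is 67.7%. The shortfall is 80 − 67.7 = 12.3 points.

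**Step 2. The protocol's interval rule.** Lower 95% bounds, ignoring correlation:

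| Interval | 77/80 | 78/80 |
|---|---|---|
| Logit-scale Wald | 89.0% | 90.6% |
| Wilson | 89.5% | 91.3% |
| Clopper-Pearson | 89.4% | 91.3% |

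All three fail at 77 and pass at 78, so each gives 67.7%. The logit-scale interval is undefined at 80/80, which is counted here as success.

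**Step 3. Can any valid test reach 80%?** The most powerful test of size exactly 0.025 rejects at 78 or more, and at 77 with probability (0.025 − 0.0107)/(0.0353 − 0.0107) = 0.581. Its power is 67.7% + 0.581 × 18.3% = 78.3%. By the Neyman-Pearson lemma, no test that holds 0.025 does better.

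**Step 4. Methods that do give 80% or more at n = 80.**

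- Arcsine formula: h = 2[arcsin√0.975 − arcsin√0.90] = 0.326; Φ(0.326 × √80 − 1.96) = 83.0%. Applied as a test, its cut-off is 77/80.
- Mid-P (0.0230 at 77/80), likelihood ratio (signed root 2.11 at 77/80) and Jeffreys: cut-off 77/80, power 85.9%, true size 0.035.
- Plain Wald: cut-off 76/80, power 95.0%, true size 0.088.

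The normal approximation with the null variance does not get there. The standard errors are √(0.09/80) = 0.03354 and √(0.975 × 0.025/80) = 0.01746, and Φ[(0.075 − 1.96 × 0.03354)/0.01746] = 70.2%.

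**Step 5. How many independent observations are needed against 90%?** Exact power first reaches 80% at n = 85 (82/85, size 0.0245, power 83.6%). It stays there to n = 92, falls to between 79.6% and 76.4% for n = 93 to 99, and is at or above 80% for every n checked from 100 to 499. At n = 100 the cut-off is 96/100, size 0.0237, power 89.4%.

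**Step 6. Power for the SAP's 80% goal, n = 80.** Cut-off 72/80, size 0.0131, power 99.98%. At the SAP's interim and final intervals (98.75% and 98.06% two-sided) the cut-off is 73/80 and power 99.9%.

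**Step 7. Illustration of clustering.** The documents give neither an intraclass correlation (ICC) nor a number of observations per patient, so both are assumed here: ICC 0.1 or 0.2, beta-binomial, true rate 97.5%, 200,000 replicates, cut-off set so that size is at most 0.025. Ten patients is the SAP's interim set; 18 is the maximum of 20 less the two stimulated on the left only.

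| Goal | Patients | 8 per patient (ICC 0.1 / 0.2) | Unlimited breaths (ICC 0.1 / 0.2) |
|---|---|---|---|
| 90% | 10 | 47% / 30% | 92% / 70% |
| 90% | 18 | 80% / 68% | 99% / 89% |
| 80% | 10 | 99% / 92% | >99.9% / 99% |

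More breaths per patient raise power, but only up to a ceiling set by the number of patients and how much they differ.

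**The case against.** The strongest reply is that the protocol never says the test is exact. The arcsine formula is a recognised method at nominal 0.025; it needs about 74 observations for 80% power and gives 83.0% at 80. A profile-likelihood interval is as natural for a logistic model as the logit-scale Wald interval; it passes 77/80 (lower bound 90.6%) and so gives 85.9%. The sponsor may well have used a method of this kind. That stands as a possible explanation of the figure, and it is a reason to ask which test was used. It does not rescue the claim as written, because these methods reach 80% only by exceeding the stated alpha.

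The second reply is that nothing turns on it. The SAP tests 80% and says the 90% goal served only for sample size. "This will be calculated for all stimulated breaths" in SAP section 11 refers to the synchrony lag, and capture is scored on the same breaths, so observations should far exceed 80. SAP sections 7 and 8 already describe the cohort, so recruitment cannot be affected. All of this is true and limits the weight of the point. The wrong figure still stands in both documents, and the relevant one, power against 80%, is missing.

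The third reply is that independence is disclosed and the analysis models within-patient correlation. This is also correct. The independence assumption is not counted as an error, and the clustering figures are an optional addition.

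**Conclusion.** The concern holds. On the plan's own inputs, 80 observations give 67.7% exact power against the 90% goal, and at most 78.3% for any test that holds one-sided 0.025. The stated figure of at least 80% is wrong as written in Protocol 6.10.3 and SAP section 2. This rests only on the documents' inputs and their independence assumption; the assumed ICC values play no part in it. The consequence is limited to an incorrect planning statement: no enrolment figure, analysis or decision rule changes, and power against the SAP's 80% goal is high. It should be corrected, but it does not threaten the study.

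**What to change.** In Protocol 6.10.3 and SAP section 2, name the test and cut-off and replace the power statement with one of these:

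- *about 68% power (exact binomial, success at 78 or more of 80, one-sided 0.025, independence assumed)*; or
- *100 observations, success at 96 or more, 89% power*.

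If 85 observations is preferred, give its cut-off (82/85, 83.6%) and note that exact power falls below 80% again at n = 93 to 99. If the original calculation used an approximate method, say which one and report its true size at n = 80.

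In the SAP, add the power for the test it will run: more than 99.9% against 80% with 80 independent observations, success at 72 or more.

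Optionally, qualify the sentence on adding observations: *extra observations from the same patients raise power only up to a limit set by the number of patients and the variation between them*. Power for 10 and 18 patients over a declared, assumed ICC range could go with it.

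The cost is wording in two places and one recalculation. The stated power against 90% becomes less favourable. No additional patients are needed.
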